3.1 Overview of Proposed Research Design

This investigation employs a randomized controlled trial (RCT) study design. Participants will be randomized into either precision pharmacotherapy, where they will receive a personally-tailored recommendation for a TUD medication based on their NMR plus standard care, or to standard care only. Standard care will adhere to the Ask-Advise-Connect model where participants are asked about tobacco use, advised to quit smoking, offered a choice of FDA-approved TUD medication and offered a referral to the Delaware Quitline for access to counseling services and medications.

Upon enrollment into the study, the research assistant will verify demographic data, administer a baseline survey, and coordinate testing for the NMR at their in-person intake visit. Patients will be randomized to the precision or standard care arms in a 1:1 ratio. Following receipt of the NMR test results and randomization, the research assistant will follow-up with a pre-quit telephonic visit to review procedures with participants. For standard care, the research assistant will provide information on FDA-approved TUD medications and offer to coordinate the process of starting on a medication of the participants' choice (i.e., nicotine patch or varenicline), which participants can decline. Participants randomized to precision pharmacotherapy will be provided with their NMR result, information on how NMR impacts TUD treatment, and a personalized recommendation for medication based on their NMR result (i.e., varenicline for faster metabolizers, nicotine patch for slower metabolizers). Similar to standard care procedures, participants will be offered either the nicotine patch or varenicline and will not be required to choose the medication based on their personalized recommendation, or any medication. For participants in both conditions who opt for medication, per participant preference, medications can be prescribed by the study physician ([name]) or the patient can be referred to the Delaware Quitline for no-cost medications, a free service available to all Delaware residents. A 1-week follow-up telephonic visit will be conducted to collect data related to medication use, quit date or smoking rate, and side-effects. Finally, a 1-month follow-up in-person visit will be arranged to complete a follow-up survey and to assess smoking status.

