3.3 Study Procedures & Data Collection

The following study procedures will be implemented. A description of the measures used to collect data during these procedures is provided below.

- **Intake Session (completed during clinic visit)**
 - Participants will complete a self-report survey of demographics, smoking history, and beliefs about the use of smoking cessation aids.
 - **[Women only]** A pregnancy screen will be administered for women capable of becoming pregnant (55 and under). NOTE: For safety reasons, pregnant women will not be eligible to participate in the research study.
 - The research assistant will complete the blood draw to be used for a nicotine metabolite ratio (NMR) test and arrange for the sample to be transported to the laboratory for processing.
- **Randomization:** Following completion of the 'intake session' and receipt of NMR testing results, participants will be randomized in a 1:1 ratio to either of the following conditions:
 - **Treatment Plan Option 1 (Standard Care):** Standard smoking cessation counseling will be offered + participant choice of nicotine patches or varenicline. Participants are also free to decline either medication.
 - **Treatment Plan Option 2 (Precision Pharmacotherapy):** Standard smoking cessation counseling will be offered + a recommendation to take either the nicotine patch or varenicline based on the results of the NMR test. Regardless of the recommendation, it would still remain the participant's choice to be prescribed either nicotine patches or varenicline. Participants are also free to decline either medication.
- **Pre-Quit Telephonic Visit:** This visit will take place after the NMR results have been received and randomization is complete, approximately 7-14 days following the intake session (depending on lab processing time).

- Participants will be informed of their treatment condition, including the recommended medication if assigned to 'treatment plan option 2' (i.e., the precision pharmacotherapy arm).
- Participants will be offered their choice of either the nicotine patch or varenicline. Participants will be reminded that taking medication is not a condition of participation in the study. In addition, participants assigned to 'treatment plan option 2' (i.e., the precision pharmacotherapy arm) will not be required to accept only the medication recommended to them based on the results of NMR testing.

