Document: Statistical Analysis Plan

Document Date: March 5, 2020

Official Study Title: A Pilot Pragmatic RCT of a Hospital-based Precision Pharmacotherapy Smoking Cessation Program

NCT#: NCT04897607

Statistical Analysis Plan

Specific Aim 1: *The proposed trial will be acceptable to underserved smokers as measured by the proportions and demographic characteristics of patients who enroll (H1.1), accept pharmacotherapy (H1.2), and complete follow-up (H1.3).*

Descriptive statistics and 95% confidence intervals will be used to summarize the feasibility metrics, namely the numbers and proportions of patients who: 1) were approached, 2) deemed eligible, 3) enrolled, 4) accepted pharmacotherapy, and 5) completed follow-up. To gain a sense of whether study participants may be considered representative of the larger population of ChristianaCare smokers as measured by race and area-level measures of SES, chi-square tests and Wilcoxon rank tests will be conducted. Race is routinely collected for all admitted patients and will permit a comparison between trial participants and the larger population of ChristianaCare smokers. However, no individual-level measures of SES are routinely collected for admitted patients and therefore will not allow for a comparison between trial participants and the larger population. Therefore, census tract measures of poverty (e.g. employment status, income, and education) based on participant residence will be used as a proxy for individual-level SES. The residential addresses for the larger population of ChristianaCare smokers has been previously geocoded and linked to census tract poverty measures,⁴⁸ which will be used to compare the proportions of participants in this trial who reside in each census tract strata.

Specific Aim 2: *Patients assigned to precision care will more readily accept pharmacotherapy (H2.1), achieve greater treatment matching (H2.2), and demonstrate improved abstinence rates (H2.3).*

Three sets of logistic regression models will be used to compare precision pharmacotherapy vs. standard care for each of the binary effectiveness outcome measures: acceptance of pharmacotherapy, treatment matching, and abstinence. Models will adjust for demographics and other covariates, including age, race/ethnicity, nicotine dependence, and indicators of SES (employment status, income, and education).

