Exploratory Aim: *Precision pharmacotherapy will improve patient outcome expectancies related to medication effectiveness and safety/side effects, which will be associated with greater use of pharmacotherapy (H3.1) and abstinence (H3.2). Higher rates of treatment matching in precision care will mitigate the reductions in abstinence rates for low-SES/racial minority smokers compared to standard care (H3.3).*

Mediation analyses. Two sets of logistic regression models will be used to evaluate whether patient outcome expectancies mediate the relationship between treatment assignment (precision vs. standard) and the outcome measures use of pharmacotherapy and abstinence. In the first step for each model, treatment condition will be used to predict the outcome measures, adjusting for the same covariates used above. In the second step, patient outcome expectancies will be used to predict the outcome measures, again adjusting for covariates. If both treatment condition and treatment expectancies are significantly associated with outcome measures, a third step will include both predictors to formally test for partial or complete mediation by assessing whether the inclusion of patient outcome expectancies reduces or eliminates the effect for treatment assignment.

Moderation analyses. A series of logistic regression models will be used to evaluate whether greater treatment matching mitigates (i.e., moderates) the lower rates of abstinence typically seen among low-SES/racial minority patients in usual care. The model will include the predictors of treatment matching (dummy coded as yes/no based on whether the participant used the medication matched to their nicotine metabolism rate: NRT for slower metabolizers, varenicline for faster metabolizers), measures of SES (e.g., years of education), and the product of these predictors. If the product, or interaction term, significantly predicts abstinence, that would provide evidence that treatment matching has differential impacts based on the SES of the participant. Post hoc analyses will be employed to describe the nature of the interaction. A

similar, albeit multilevel approach will be used to test for interaction between area-level variables (e.g., census tract poverty levels, tobacco outlet density) and treatment matching.

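### The exploratory aim says precision care improves outcome expectancies, but no SAP model tests this; the arm-plus-expectancy model is run only after two significant results, and no indirect effect is defined.

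*SAP*

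**What the plan says.** The exploratory aim begins: "Precision pharmacotherapy will improve patient outcome expectancies related to medication effectiveness and safety/side effects". It goes on to say that expectancies will be associated with greater medication use (H3.1) and abstinence (H3.2).

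The mediation plan has three steps:

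1. "In the first step for each model, treatment condition will be used to predict the outcome measures, adjusting for the same covariates used above".
2. "In the second step, patient outcome expectancies will be used to predict the outcome measures, again adjusting for covariates". The covariates are those listed under Specific Aim 2 (age, race/ethnicity, nicotine dependence, SES indicators). Arm is not among them.
3. "If both treatment condition and treatment expectancies are significantly associated with outcome measures, a third step will include both predictors". The SAP calls this a formal test of partial or complete mediation. Its criterion is "assessing whether the inclusion of patient outcome expectancies reduces or eliminates the effect for treatment assignment".

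Under Specific Aim 2, "Three sets of logistic regression models will be used to compare precision pharmacotherapy vs. standard care for each of the binary effectiveness outcome measures"; these outcomes are acceptance of medication, treatment matching and abstinence.

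On measurement, Protocol 3.3 has this at intake, before randomisation: "Participants will complete a self-report survey of demographics, smoking history, and beliefs about the use of smoking cessation aids". The schedule of measures in 3.3 has no expectancy row. Protocol 3.1 mentions a later survey without giving its content: "Finally, a 1-month follow-up in-person visit will be arranged to complete a follow-up survey and to assess smoking status".

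**The concern.** Mediation needs two links: arm must shift expectancies, and expectancies must relate to the outcome once arm is held fixed. The plan never estimates the first. It estimates the second only if a significance gate is passed, and that gate requires a significant total arm effect with about 50 participants per arm.

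The most likely result is therefore that the mediation question goes unanswered, even if expectancies do carry the effect. If step 3 is reached, the reader sees one coefficient beside another with no measure of uncertainty. For a pilot meant to show whether the proposed mechanism is plausible, an estimate of each path with its interval is more useful than a sequence of significance decisions.

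**Working it through.** **1. Outcome of each model in the SAP.**

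| SAP analysis | Outcome | Arm in model | Expectancies in model |
|---|---|---|---|
| Aim 2 models | acceptance, matching, abstinence | yes | no |
| Mediation step 1 | medication use, abstinence | yes | no |
| Mediation step 2 | medication use, abstinence | no | yes |
| Mediation step 3 (gated) | medication use, abstinence | yes | yes |
| Moderation | abstinence | not listed | no |

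Aim 1 consists of feasibility proportions and representativeness comparisons. Expectancies are never an outcome. This finding needs no numbers.

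**2. How hard the gate is to pass.** The documents state no alpha, power or effect size, so there is no planned figure to reproduce. From the documents: about 100 participants (Protocol 2.0), 1:1 allocation (3.1), and cessation rates that rarely exceed 25% in hospital programmes (Protocol background). Assumed: two-sided 5%.

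Step 1 power = Φ{[|p₂−p₁| − 1.96√(2p̄(1−p̄)/50)] / √((p₁(1−p₁)+p₂(1−p₂))/50)}.

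- Abstinence 25% v 35%: (0.10 − 1.96×0.0917)/0.0911 = −0.87, power 19%.
- Abstinence 25% v 45%: (0.20 − 1.96×0.0954)/0.0933 = 0.14, power 56%.
- Medication use 50% v 70%: (0.20 − 1.96×0.0980)/0.0959 = 0.08, power 53%.

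The gate passes half of trials only when the true arm difference is about 17–20 points.

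**3. The gate against testing both paths.** Write a for the arm shift in expectancies (SD units) and b for the log-odds ratio per SD. Under full mediation the total arm log-odds ratio is roughly a×b, from 0.5×0.6 = 0.30 to 0.8×1.0 = 0.80. At 25% abstinence its standard error is about √(2/(50×0.25×0.75)) = 0.46, so z is about 0.65 to 1.7, short of 1.96. Path a alone has standard error √(2/50) = 0.20 SD, so z is 2.5 to 4.0.

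Simulation (n = 100, no covariates, Wald tests, 6,000 replicates). Each cell is step 3 reached / joint test of both paths significant:

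| Control rate | a 0.5, b 0.6 | a 0.5, b 1.0 | a 0.8, b 0.6 | a 0.8, b 1.0 |
|---|---|---|---|---|
| 18% (assumed) | 6% / 43% | 12% / 68% | 11% / 61% | 28% / 94% |
| 25% | 8% / 49% | 16% / 68% | 15% / 69% | 33% / 96% |
| 50% (assumed, medication use) | 11% / 54% | 18% / 70% | 19% / 79% | 38% / 97% |

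Repeat runs agree to within about two points. With six covariates the pattern holds: 7–30% v 38–94% for abstinence and 10–34% v 51–94% for medication use.

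Other assumptions change the picture. With weak paths (a 0.3, b 0.5) both are low: 3–5% v 15–21%. With a direct arm log-odds ratio of 0.5 added, step 3 is reached in 27–74%.

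**4. The change-in-coefficient criterion.** Logistic coefficients shift when a predictor of the outcome is added, even without mediation. With a = 0, a conditional arm log-odds ratio of 1.00 and intercept −1.6, the unadjusted coefficient is 0.89 when b = 0.8 and 0.79 when b = 1.2. This shift runs opposite to mediation, so a true reduction can be hidden.

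**5. The missing model is feasible at this size.** The 95% half-width for the arm difference in expectancies is about 1.98×0.20 = 0.40 SD. Power is 70% at 0.5 SD and 98% at 0.8 SD.

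**The case against.** Several points on the other side stand.

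- A reader might infer that H3.1 and H3.2 go untested. They do not: both are worded as associations, and step 2 estimates those with no gate, though without adjusting for arm. What lacks a model is the aim's opening clause.
- A reader might infer that the SAP plans no test of mediation at all. It does call step 3 a formal test. The defect is that the test is left undefined beyond a bare change in coefficient.
- A reader might infer that the plan will often declare false mediation. The figures do not support this. With no arm effect on expectancies, b = 1 and a direct log-odds ratio of 0.5–1.0, any reduction after passing the gate appears in about 4–10% of trials.
- The percentages rest on assumed effects, and reaching step 3 is not the same event as detecting an indirect effect. It is, however, a precondition for any mediation result under the plan, so the comparison is if anything generous to it.
- Measurement may be the tighter limit. Without a score taken after disclosure, no analysis can rescue the aim. The documents do not show that such a score is absent, because the one-month survey is undefined; they only fail to describe one.

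**Conclusion.** The point holds. The opening clause of the exploratory aim has no model, the arm-adjusted expectancy path is estimated only after two significant results, and no indirect effect, interval or test statistic is defined. Those three statements follow from the SAP text alone.

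The size is illustrative. At n = 100, two-sided 5%, full mediation and moderate to strong paths, the gate opens in about 5–39% of trials, against about 43–96% detection by testing both paths. The gap narrows with weak paths or a direct arm effect.

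The consequence is confined to an exploratory aim in a pilot. Reading it as a threat to the trial's main conclusions would be wrong: Aims 1 and 2 are unaffected. It should be corrected because the remedy is cheap.

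**What to change.** Replace the gated sequence with two models, fitted whatever the significance of steps 1 and 2:

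- **(a)** Each expectancy domain (effectiveness; safety/side effects) on arm plus covariates, adding the intake score if it is the same instrument. This is the test of the opening clause.
- **(b)** Outcome on arm, expectancy and covariates.

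Report the indirect effect with a bootstrap 95% interval, preferably as a risk difference. Label it exploratory and state the assumption of no unmeasured expectancy–outcome confounding. Use a reduced covariate set or a penalised (Firth-type) fit: with covariates and 18% control abstinence, 12–16% of resamples showed signs of separation.

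State in the SAP which expectancy score is used and when it is taken. Model (a) needs a score after arm disclosure; mediation also needs it to precede the outcome. A score from the one-month visit could serve (a) but not mediation, because it is taken when smoking status is assessed and after the medication choice. If no suitably timed score exists, report mediation as not estimable. If there is no post-disclosure score at all, say that the opening clause cannot be tested.

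The cost is SAP rewording and modest programming. Intervals will be wide, roughly 13–23 percentage points with covariates. Adding expectancy items would be an optional protocol change; items placed between disclosure and the medication offer could themselves influence acceptance (H2.1).

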Approximately 100 adult current smokers (≥ 5 cigarettes/day), who are patients at the Helen F. Graham Cancer Center & Research Institute (Christiana Care) lung/thoracic clinic who are ages 18 and older. Exclusion criteria include: 1) use of non-cigarette tobacco products or current TUD treatment, 2) psychiatric or other medical contraindications to receiving TUD medication (assessed by the study physician), 3) no telephone, 4) medical instability, 7) inability to communicate in English, 8) unable to consent due to mental status, 9) estimated life expectancy of < 6 months, 10) pregnancy.

The duration of study participation will be approximately 6 weeks from the first through the final study visit.

3.0 STUDY PROCEDURES:

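### The mediation analysis can conclude complete mediation with no interval or margin for the remaining direct effect; at about 50 per arm, a non-significant arm term is weak evidence that the effect has gone

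*SAP*

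**What the plan says.** The SAP, under Exploratory Aim, Mediation analyses, sets out three logistic regression steps for each of two binary outcomes: "the outcome measures use of pharmacotherapy and abstinence".

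- Step 1: "In the first step for each model, treatment condition will be used to predict the outcome measures", with covariates.
- Step 2: expectancies predict the same outcomes, with the same covariates.
- Step 3 depends on the first two: "If both treatment condition and treatment expectancies are significantly associated with outcome measures, a third step will include both predictors". Its purpose is to "formally test for partial or complete mediation by assessing whether the inclusion of patient outcome expectancies reduces or eliminates the effect for treatment assignment".

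No significance level, interval, margin or definition of elimination is given. On sample size, section 2.0 of the Protocol gives "Approximately 100 adult current smokers" and section 3.1 says "Patients will be randomized to the precision or standard care arms in a 1:1 ratio", so there are about 50 per arm. Neither document states an effect size or power.

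**The concern.** Complete mediation is a claim of no effect: with expectancies held fixed, precision care does nothing more. A fitted coefficient is never exactly zero, so the analyst must supply a rule for deciding that the arm effect has been eliminated. The paragraph's only decision language is significance ("significantly associated with outcome measures") and step 3 is described as a formal test, so the analyst is likely to ask whether the arm's p-value is still below 0.05. That accepts the null hypothesis for the direct effect from a model with little power to reject it.

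At stake is an overstated role for expectancies. The SAP itself expects another route to abstinence, treatment matching (H2.2 and H3.3), and a false finding of complete mediation would wrongly discount it. This argument applies to abstinence. Matching has no evident bearing on the other outcome, use of pharmacotherapy.

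**Working it through.** The plan has no figure of its own to reproduce.

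**Inputs from the documents.** About 100 participants, 1:1, binary outcomes, logistic models, and step 3 only if steps 1 and 2 are both significant.

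**Assumptions.** Two-sided 0.05. Expectancies are normal with SD 1 and shifted by *a* SD in the precision arm. *Half direct* means that half of the total arm effect on the log-odds scale does not pass through expectancies. *Complete* means that steps 1 and 2 are significant and the arm p-value in step 3 is at least 0.05. The arm rates are assumed. The Protocol's background says only that rates in hospital-based programmes seldom pass 25%.

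**1. Precision of the arm term, by hand.** Unadjusted SE of the log odds ratio = sqrt(1/[n p0(1−p0)] + 1/[n p1(1−p1)]), with n = 50.

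- 50% v 75%: sqrt(1/12.5 + 1/9.375) = 0.432. The 95% CI runs a factor of exp(1.96 × 0.432) = 2.3 either side of the estimate.
- 15% v 35%: sqrt(1/6.375 + 1/11.375) = 0.495, a factor of exp(1.96 × 0.495) = 2.6.

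A direct odds ratio of 1.80 gives z = ln(1.80)/0.432 = 1.36 in the first case. The chance of non-significance is about 1 − Φ(1.36 − 1.96) = 73%. In the second, a direct odds ratio of 1.81 gives z = 0.593/0.495 = 1.20 and about 78%. Simulation with six covariates and the mediator in the model gave 76% and 81%.

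**2. Power to enter step 3.** Usual two-proportion formula, 50 per arm: 25% v 40%, 0.36; 25% v 45%, 0.56; 25% v 50%, 0.74; 50% v 75%, 0.74.

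**3. The three steps simulated, half direct, N = 100, no covariates** (*a* = 0.5 / 0.8 / 1.2 SD):

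| Arm rates | Complete, given step 3 reached | Complete, all trials |
|---|---|---|
| 25% v 40% | 0.63 / 0.73 / 0.80 | 0.21 / 0.21 / 0.20 |
| 25% v 45% | 0.61 / 0.69 / 0.76 | 0.33 / 0.35 / 0.36 |
| 25% v 50% | 0.57 / 0.66 / 0.74 | 0.42 / 0.49 / 0.51 |
| 50% v 75% | 0.57 / 0.66 / 0.73 | 0.42 / 0.48 / 0.51 |

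The columns are linked by the chance of reaching step 3. For 25% v 50% with *a* = 0.8, 0.736 × 0.670 = 0.49.

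**4. Sensitivity, half direct.** The first three figures are conditional on reaching step 3.

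- Half defined on the risk-difference scale (*a* = 0.5 to 0.8): 54% to 71%.
- Eight covariates: 53% to 69% at N = 100.
- Eight covariates: 57% to 69% at N = 80.
- Six covariates, expectancy odds ratio 1.8 or 2.5 per SD, rates 15% v 35%, 50% v 75% or 40% v 70%: 59% to 72% conditional and 34% to 55% of all trials.

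**5. Where the figure falls** (conditional on reaching step 3).

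- Very large total effects, half direct, *a* = 0.5 / 0.8 / 1.2: 50% v 80%, 0.36 / 0.56 / 0.66; 25% v 60%, 0.15 / 0.50 / 0.59.
- Small shift, *a* = 0.3, half direct: 0.45 to 0.60 for differences up to 25 points.
- Three quarters direct: 21% to 39% in one set of scenarios, 34% to 53% in another.
- No effect through expectancies (100% direct): 2% to 5%.

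**The case against.** **The criterion is not in the text.** The SAP speaks of "assessing whether the inclusion of patient outcome expectancies reduces or eliminates the effect for treatment assignment". It does not say that a p-value above 0.05 means complete mediation. A reader might infer that this is the written rule, and the documents do not support that. What they support is that complete mediation is a planned conclusion, that a formal test is meant to deliver it, and that nothing protects it from this reading. If a change in the size of the effect was meant, the threshold is still missing.

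**Most trials would not carry the label.** A reader might infer that a trial of this size would report complete mediation most of the time. That holds only among trials that pass steps 1 and 2. In two worked cases, 68% × 69% = 47% and 58% × 72% = 42% of all trials. The conditional figure is still the relevant one for the wording, because the label can be issued only in step 3.

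**The expectancy shift is an assumption.** With expectancy odds ratios of 1.8 or 2.5 per SD, a half-direct effect needs a shift of about 0.6 to 1.15 SD, which is large for a telephone visit. At 0.3 SD with the same odds ratios and arm rates, 77% to 87% of the effect is direct. The label is then given in 10% to 25% of trials reaching step 3, and in 7% to 15% overall. This stands as a limit on the size.

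**The mediator may not be measured after randomization.** Section 3.3 of the Protocol describes beliefs about cessation aids only at intake, and its measures table lists no later expectancy score. Section 3.1 mentions a follow-up survey without giving its content. If there is no later score, the arm cannot shift it and the label would be rare (2% to 5%). That is a separate problem. The SAP analysis presupposes a score that treatment can change.

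**The consequences are limited.** This is an exploratory aim in a pilot, and H3.1 and H3.2 do not hypothesize complete mediation. A reader might infer that the result would decide whether messaging can replace NMR testing. No section makes that the trial's question or ties a later decision to it.

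**Conclusion.** The concern holds as a defect in the decision in step 3. The plan allows a conclusion of no direct effect without any interval or margin to support it, and its only decision language points to significance. With half of the effect direct, differences of 15 to 25 points and a shift of about 0.5 SD or more, the adjusted arm term is non-significant in roughly 55% to 80% of trials that reach step 3. That is about 19% to 51% of all trials, rising to about 55% at a 30-point difference. All effect sizes and the 0.05 level are assumptions, and small shifts or very large total effects bring the conditional figure to half or below.

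The exploratory label lowers the weight of the result. It does not turn a non-significant term into evidence of no effect.

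**What to change.** In the SAP's Mediation analyses, replace the step 3 decision between partial and complete mediation with the following:

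- Report the arm odds ratio adjusted for expectancies and covariates, as the direct effect, with its 95% CI.
- State that a non-significant direct effect will not be read as complete mediation.
- When the direct effect is non-significant, report that a remaining direct effect up to the upper limit of the CI cannot be excluded.

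The cost is a few sentences of SAP text. The model is already planned, and no new data or visits are needed. The downside is that the trial gives up a complete-mediation claim. With a CI running a factor of about 2.3 to 2.6 either side of the estimate even before adjustment, it could not support that claim at this size.

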Tobacco use is the leading preventable cause of morbidity and mortality in the United States (US) and Delaware,¹ claiming more than 400,000 US lives each year.² Tobacco use disorder (TUD), or the long-term problematic use of tobacco, has been recognized by the American Psychiatric Association as a substance use/behavioral health condition (see ³). The burdens of TUD disproportionately affect racial minorities and those with low socioeconomic status (SES), thereby contributing to tobacco-related health disparities (TRHDs).⁴ Underserved smokers are no less interested in quitting smoking and make just as many quit attempts as more advantaged smokers⁵ but are less likely to be advised to quit,⁶ have less access to treatment,⁷ use evidence-based treatments less frequently, report greater concerns about the safety of these medications, and ultimately experience lower abstinence rates.⁵ Hospital-based smoking cessation interventions have the potential to reach large segments of this underserved population. A Cochrane review found that hospital-based interventions significantly increase smoking cessation rates compared to usual care;⁸ however, rates rarely exceed 25%. Promising new evidence suggests that applying a *precision pharmacotherapy* approach based on the nicotine metabolite ratio (NMR), a commercially available, genetically-informed marker of nicotine metabolism rate can significantly improve cessation outcomes. Evidence from multiple independent studies,⁹⁻¹² including a recent randomized clinical trial (RCT),¹³ demonstrates that matching slow metabolizers of nicotine with the nicotine patch and fast metabolizers of nicotine with varenicline can maximize treatment response and minimize side effects. While encouraging, a critical gap in knowledge is how to best translate a precision pharmacotherapy approach into a hospital-based smoking cessation intervention and improve cessation rates for underserved smokers. Preliminary data suggest that personalized treatment recommendations may increase TUD medication uptake and effectiveness.^{14,15} Thus, the scientific premise of this application is that integrating a precision pharmacotherapy approach into a hospital-based TUD treatment program will increase medication uptake and effectiveness, with particular relevance for smokers from underserved communities.

2.0 STUDY POPULATION:

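### The SAP's mediation rule compares logistic arm effects with and without expectancies, so it mixes mediation with rescaling and tends to understate partial mediation (minor, exploratory aim)

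*SAP*

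**What the plan says.** The SAP's Exploratory Aim, under Mediation analyses, states that "Two sets of logistic regression models will be used to evaluate whether patient outcome expectancies mediate the relationship" between treatment assignment and two outcomes, use of pharmacotherapy and abstinence.

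- Step 1 fits the arm, "adjusting for the same covariates used above", meaning the demographic, dependence and SES covariates of Aim 2.
- Step 2 fits expectancies, again with covariates.
- The last step is conditional: "If both treatment condition and treatment expectancies are significantly associated with outcome measures, a third step will include both predictors". Partial or complete mediation is then judged by "assessing whether the inclusion of patient outcome expectancies reduces or eliminates the effect for treatment assignment".

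The only effect scale that the SAP implies is the logistic one. It plans no rescaling, no risk-scale effect, and no estimate or interval for the indirect effect.

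On size, section 2.0 of the protocol gives "Approximately 100 adult current smokers", and section 3.1 says "Patients will be randomized to the precision or standard care arms in a 1:1 ratio". On timing, section 3.3 of the protocol lists a survey of beliefs about cessation aids at the intake session, before randomisation. Its table of measures has no expectancy row at any visit. Section 3.1 mentions a follow-up survey at one month, but section 3.3 lists only medication use, quit date or smoking rate, and side effects for that visit.

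**The concern.** In a linear model, the fall in the arm coefficient when a mediator is added equals the indirect effect. In a logistic model it does not. Adding a variable that predicts the outcome but is independent of arm moves a non-zero arm log-odds ratio away from zero, with no confounding and no mediation. When the added variable is a true mediator, this shift works against the fall that the rule looks for. The observed change is mediation minus a scale artefact, and the SAP has no means of separating them.

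H3.1 and H3.2 are decided by this rule. A modest expectancy pathway could be dismissed just when the pilot's results are used to plan a larger study.

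**Working it through.** The documents give no effect size, power or mediation figure, so there is nothing of the plan's own to reproduce. All effect inputs below are assumptions.

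**Model.** Expectancy score M = a × arm + N(0,1), and logit P(Y) = b0 + c′ × arm + b × M. The step 3 arm effect is c′. The step 1 arm effect c is the log-odds ratio after averaging each arm's risk over M (80-point Gauss–Hermite integration). Two shares are compared:

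- the SAP's raw change, (c − c′)/c;
- the same-scale share, ab/(c′ + ab), which is what the Karlson–Holm–Breen (KHB) rescaling targets.

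**Assumed values.** Abstinence: b0 = −1.7, c′ = 0.70. Medication use: b0 = 0.2, c′ = 0.95. With b = 1.0 the control risks are 19.3% and 54.1%.

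| Outcome | b per SD | Shift a (SD) | c (step 1) | c′ (step 3) | Raw change in arm effect | Same-scale share |
|---|---|---|---|---|---|---|
| Abstinence | 1.0 | 0 | 0.598 | 0.700 | rises 17.0% | 0% |
| Abstinence | 1.0 | 0.1 | 0.682 | 0.700 | rises 2.6% | 12.5% |
| Abstinence | 1.0 | 0.2 | 0.766 | 0.700 | falls 8.6% | 22.2% |
| Abstinence | 1.0 | 0.4 | 0.933 | 0.700 | falls 25.0% | 36.4% |
| Use | 1.0 | 0 | 0.793 | 0.950 | rises 19.8% | 0% |
| Use | 1.0 | 0.1 | 0.878 | 0.950 | rises 8.2% | 9.5% |
| Use | 1.0 | 0.2 | 0.963 | 0.950 | falls 1.4% | 17.4% |
| Use | 1.0 | 0.4 | 1.135 | 0.950 | falls 16.3% | 29.6% |
| Abstinence | 0.5 | 0.4 | 0.862 | 0.700 | falls 18.8% | 22.2% |
| Use | 0.5 | 0.4 | 1.093 | 0.950 | falls 13.1% | 17.4% |

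Example (abstinence, b = 1.0, a = 0.4): raw (0.933 − 0.700)/0.933 = 25.0%; same-scale 0.4/(0.4 + 0.7) = 36.4%; gap 11.4 points. For use the gap is 29.6 − 16.3 = 13.3 points. At b = 0.5 the gaps are 22.2 − 18.8 = 3.4 and 17.4 − 13.1 = 4.3 points.

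**Risk scale.** For abstinence with b = 1.0 and a = 0, the risks are 19.3% and 30.3%. The standardised risk difference is 11.0 points with or without expectancies, so there is no artefact. With a = 0.4 the total difference is 37.8 − 19.3 = 18.5 points, and the indirect share is 32% to 41%, depending on the order of decomposition. The raw fall is 25%.

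**Wider grid.** Control risk 15%, 25%, 50%; a = 0.2, 0.5, 0.8; odds ratio per SD of 1.5, 2, 3, 5; direct odds ratio 1.5, 2, 3: 3 × 3 × 4 × 3 = 108 cells. The raw share was below the same-scale share in all 108. The arm effect actually rose in 5, all with a = 0.2, odds ratio per SD of 3 or more, and direct odds ratio 3. With a direct odds ratio of 1 (complete mediation), both shares are 100%.

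**Simulation at 50 per arm.** 4,000 trials per scenario; control risk 25%; direct odds ratio 2; two-sided 0.05 Wald gate; no covariates or dropout.

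- a = 0.2: among trials that passed the gate, the arm effect rose in 31% (odds ratio 2 per SD) and 40% (odds ratio 3), despite true mediation.
- a = 0.5: among trials that passed the gate, the arm was non-significant at step 3 in 0.470 (odds ratio 2) and 0.555 (odds ratio 3). The true same-scale shares were only 33.3% and 44.2%.

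**The case against.** The SAP's rule is qualitative. It asks whether the arm effect is reduced or eliminated and promises no proportion mediated. In 103 of the 108 grid cells the population effect does fall, so the qualitative answer is usually right. This stands, and it limits the point to understated size and to weak pathways.

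A reader might infer that adding any outcome predictor raises the arm effect, so that real mediation is generally hidden. The documents and the arithmetic do not support that. The rise holds for a predictor independent of arm. A mediator depends on arm, and the net effect usually falls, though by too little. Complete mediation is not masked.

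A reader might also infer that the error always runs downward. It does so only against the same-scale benchmark. Against a risk-difference share the raw fall can be higher: 20.1% against 18.6% at control risk 50%, a = 0.8, odds ratio 1.5 per SD and direct odds ratio 3. If elimination is read as loss of significance, the rule errs towards overstating mediation, as the simulation shows. The SAP does not say which reading applies.

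Sampling noise is also larger than the bias. In simulations of the 0.4 SD scenarios with 100 participants, the 10th-to-90th percentile range of the raw share, among trials passing the gate, spanned roughly 25 to 42 points. That is a reason to require an interval. It does not justify keeping a rule that mixes two quantities.

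Finally, the timing of the expectancy measure may matter more than the scale. The only listed measure of beliefs precedes randomisation, and such a score cannot carry the arm's effect. That is a separate gap, and the scale remedy is useful only once it is closed.

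**Conclusion.** The concern holds in limited form. The planned change in the logistic arm effect mixes mediation with rescaling. Relative to a same-scale measure, partial mediation is understated by about 11 to 13 points of share at an assumed log-odds ratio of 1.0 per SD and a 0.4 SD shift, and by 3 to 4 points at 0.5 per SD. With a strong predictor and a shift of about 0.1 to 0.2 SD, the fall can vanish or reverse.

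These sizes rest on an assumed normal mediator, no arm-by-mediator interaction, no mediator–outcome confounding, and effect values that the documents do not supply. The non-collapsibility itself does not depend on the chosen values. Severity is minor: no Aim 1 or Aim 2 conclusion is affected, and the aim is exploratory in a pilot of about 100 participants.

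**What to change.** In the SAP's Mediation analyses, replace the comparison of arm effects and the partial/complete label with an estimated indirect effect on a common scale, for each outcome. Either of these would do:

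- the KHB-rescaled log-odds: refit step 1 with the residual of expectancies on arm and covariates included, then compare its arm coefficient with that of step 3;
- the arm's standardised risk difference from the models with and without expectancies.

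Report the indirect effect with a bootstrap 95% interval, and do not read significance or its loss at step 3 as evidence on mediation. State that the expectancy score used is measured after randomisation, and name the visit.

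If such a score exists, the cost is SAP wording and a little code. If the intake survey is the only source, a post-randomisation measure must first be added to section 3.3 of the protocol; otherwise the mediation analysis should be withdrawn.
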